This protocol is associated with an Investigational New Drug Application ("IND") sponsored by [name] at Moffitt Cancer Center. IND Safety Reports are required for any adverse experience associated (or possibly associated) with the use of the investigational product(s) that is both serious and unexpected. To meet the IND Safety Reporting requirements set forth in 21 CFR §312.32, FDA Form 3500A (MedWatch form) will be completed and provided to the Moffitt Office of Institutional Regulatory Affairs for Investigational Drugs and Devices. All other adverse events will be reported to the FDA as part of the annual reporting requirement of the IND.

The initial report will be as complete as possible, including details of the current illness and serious adverse event, and an assessment of the causal relationship between the event and the investigational product(s). Information not available at the time of the initial report (e.g., an end date for the adverse event or laboratory values received after the report) will be documented on a follow-up report. A final report to document resolution of the serious adverse event is required if it is not documented in the initial report.

The Moffitt Office of Institutional Regulatory Affairs will complete the necessary documents and provide the report to the FDA as an official submission to the IND. This will occur independently of any other use of the MedWatch form or required reporting of serious adverse events. Submission of the MedWatch form to any other agency, including the FDA, does not fulfill this IND Safety Reporting requirement. Follow-up to

the safety report must also be submitted to the Office of Institutional Regulatory Affairs in a timely manner.

Upon completion of the report, a copy of all initial and follow-up MedWatch forms will be FAXed to the Manager of the Office of Institutional Regulatory Affairs [contact]) and a telephone call or email will be made to confirm receipt.

For unexpected fatal or life threatening experiences associated with the use of the investigational product(s), the Office of Institutional Regulatory Affairs will be contacted within 24 hours. Notification to the FDA will be made as soon as possible, but no later than 7 calendar days after initial receipt of the information.

Data Safety and Monitoring Plan

The Data Safety & Monitoring Plan (DSMP) will ensure that this trial is well designed, responsibly managed, appropriately reported, and that it protects the rights and welfare of patients. The following internal and external review and monitoring processes provide oversight and active monitoring of this trial:

- The Principal Investigators (PI)
- The Scientific Review Committee (SRC)
- The Protocol Monitoring Committee (PMC)
- The Research Compliance Division of the Cancer Center's Compliance Office (RCD)
- Institutional Review Board (IRB)

The protocol includes what constitutes an adverse event (versus what is a serious adverse event), the entities to which adverse events should be reported, the timing of this reporting, and the person or persons responsible for reporting.

Initial and Ongoing Monitoring and Review

Principal Investigator (PI)

The PI of the study has primary responsibility for ensuring that the protocol is conducted as approved by the SRC and the IRB. The PI will review weekly with the trial coordinator patient eligibility and accrual. The PI will continuously monitor data both for efficacy and toxicity through weekly meetings conducted together with the clinical trial coordinator, and in monthly review of data in the Moffitt BMT Program research meeting. The PI will also be responsible for monitoring recorded data for accuracy through review of primary clinical records. The PI will ensure that the monitoring plan is followed, that all data required for oversight of monitoring are accurately reported to the Scientific Review Committee (SRC), Protocol Monitoring Committee (PMC) and IRB as required, and that all adverse events are appropriately reported.

The Scientific Review Committee (SRC)

The Cancer Center's internal Scientific Review Committee (SRC) provides for a formal internal peer review of all protocols and general scientific oversight of interventional clinical research. The Committee has a defined membership representing all of the major research divisions of the Cancer Center, including biostatisticians. All new protocol submissions must contain the required elements of the protocol, and must include a DSMP prior to approval by the Committee. The plan has to be appropriate for the phase and risk of the proposed study.

The Protocol Monitoring Committee (PMC)

The Protocol Monitoring Committee (PMC) will monitor this trial for safety, progress, protocol compliance, accrual, adverse event reporting, and data integrity. The membership of the PMC includes physician representation from each program area and a biostatistician. In addition to the existing stopping rules, the PMC is authorized to suspend a trial for non-compliance with a DSMP or as a result of audit findings deemed unacceptable. The PMC will report significant findings to the IRB, and applicable regulatory bodies. Interim meetings are scheduled to address specific issues that require immediate attention to ensure safety of research participants.

Phase I: Safety and monitoring reports are to be submitted to the Protocol Monitoring Committee (PMC) after completing each odd numbered dose level (i.e., 1, 3, 5, etc), or more frequently if requested by the PMC. A final safety and monitoring report must be submitted to the PMC within three months of defining the maximum tolerated dose (MTD).

Phase II: Safety and monitoring reports are to be submitted to the Protocol Monitoring Committee (PMC) once 30% of the total accrual has been met or once the early stopping rule threshold has been met. A final safety and monitoring report must be submitted to the PMC within three months of last subject enrollment.

The Research Compliance Division of the Cancer Center's Compliance Office (RCD)

The Cancer Center's Research Compliance Division (RCD) of the Corporate Compliance Department coordinates internal audits of all investigator-initiated trials conducted at the Cancer Center and its affiliates. The frequency of the audits is driven by the rate of accrual on a specific trial as well as the perceived patient risk for participating in the trial. Internal audits are conducted by the RCD in accordance with applicable regulatory standards.

The purpose of the internal audit program is to:

- Ensure protocol compliance and the validity and integrity of data, thereby promoting patient safety and maintaining scientific validity
- Recommend modification of research practices as necessary and provide education on issues that are critical to good research practices

The following elements of trial documentation may be incorporated into this review:

- Source documentation verification of eligibility and compliance with the protocol
- Compliance with adverse and serious adverse event reporting standards
- Regulatory review of IRB compliance and external reporting requirements
- Drug/device accountability and handling
- Completeness and quality of data

RCD auditors report findings to the PI and PMC, as appropriate, for review and audit determinations along with a statement from the PI. The PI is encouraged to proactively implement corrective actions to remedy any deficiencies noted in the audit. The PMC determines the findings as one of the following: *Acceptable*, *Acceptable with corrective action*, *Tabled for Additional Information*, or *Unacceptable*. The PI and IRB are then informed of the audit determinations made by the PMC. The PI and IRB are then informed of the audit determinations made by the PMC. Audit results may then be presented to the Corporate Compliance Steering Committee, chaired by the Center Director, and to the Joint Corporate Compliance Committee of the Board

Trial monitoring by Moffitt Monitoring Core (MMC)

Trial monitoring by the Moffitt Monitoring Core (MMC) will verify that the rights and wellbeing of human subjects enrolled in specific Moffitt sponsored principal investigator (PI) initiated clinical research are protected. PI initiated clinical trials will be monitored on-site regularly to verify the reported trial data is accurate, complete, and verifiable from source documents; and the conduct of the trial is in compliance with the currently approved protocol/amendments, data safety-monitoring, Good Clinical Practice (GCP), and applicable regulatory requirements. Routine monitoring visits will be conducted, at a minimum, annually.

Institutional Review Board (IRB)

The trial will not be initiated without approval of the appropriate Institutional Review Board (IRB). All administrative requirements of the governing body of the institution will be fully complied with. This protocol, consent procedures, and any amendments will be approved by the IRB in compliance with current regulations of the Food and Drug Administration prior to initiation unless necessary to protect the safety and welfare of subjects; in which case, the IRB will be notified within 24 hours of implementing the change. The IRB will be kept informed by the investigator as to the progress of the study as well as to any serious or unusual adverse events.

Protocol amendments or changes in study conduct

Any change or addition (excluding administrative) to this protocol requires a written protocol amendment that will be reviewed and approved by the Moffitt Cancer Center SRC and the Institutional Review Board (IRB).

Data management

Data collection

Investigators must enter the information required by the protocol onto Case Report Forms (CRFs).

Records to be kept

Data will be kept confidential and will be entered into Oncore and the BMT research database. In computer generated reports for external review, patients will only be referred to by a unique identification number.

Both Oncore and the BMT research database is password protected and limited only to designated personnel. In order to assure quality, both physicians and clinical research personnel regularly audit specified data that is manually entered into the system.

Representatives of the IRB, the FDA, and other governmental regulatory authorities will have access to patient information as it pertains to the study. Privacy and confidentiality of the information will be protected to the extent provided by law.

Ethics and Good Clinical Practice

This study will be carried out in compliance with the protocol and the principles of Good Clinical Practice, as described in:

- ICH Harmonized Tripartite Guidelines for Good Clinical Practice 1996. Directive 91/507/EEC, The Rules Governing Medicinal Products in the European Community.
- US 21 Code of Federal Regulations dealing with clinical studies (including parts 50 and 56 concerning informed consent and IRB regulations).
- Declaration of Helsinki and amendments, concerning medical research in humans (Recommendations Guiding Physicians in Biomedical Research Involving Human Subjects).

The investigator agrees to adhere to the instructions and procedures described in it and thereby to adhere to the principles of Good Clinical Practice that it conforms to.

Informed consent

The investigator and/or designated members of the research study team will explain to each subject the nature of the study, its purpose, the procedures involved, the expected duration, the potential risks and benefits involved and any discomfort it may entail. Each subject will be informed that participation in the study is voluntary and that he/she may withdraw from the study at any time and that withdrawal of consent will not affect his/her subsequent medical treatment or relationship with the treating physician.

This informed consent will be given by means of a standard written statement, written in non-technical language. The subject will read and consider the statement before signing

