6. In setting of increase chronic GVHD activity upon taper, increase prednisone dose as needed, with upper limit of 1-2mg/kg/day
7. Following complete discontinuation of prednisone, begin taper of other immune suppressive agents as tolerated.

ii. Ofatumumab

Ofatumumab Administration

Ofatumumab will be administered by IV infusion, with cohort-dependent dosing in the phase I dose escalation component of this study. Following definition of the ofatumumab MTD in the phase I component, this dose will be carried forward as the recommended phase II dose.

The following dose cohorts to be tested in the phase I component:

(cohort -1): 100mg days 0 and 14

cohort 1: 300mg days 0 and 14

cohort 2: 700mg days 0 and 14

cohort 3: 1000mg days 0 and 14

****cohort/dose level -1 (100mg days 0 and 14) will be pursued only if 2/3 patients in cohort 1 (300mg days 0 and 14) experience DLT.***

The following instructions are to be followed for infusion of ofatumumab:

Pre-medication before each ofatumumab infusion must be given within 30 minutes to 2 hours prior to the treatment:

Pre-medication Requirements prior to Ofatumumab Infusions

Infusion #	Acetaminophen (po) or equivalent	Antihistamine (iv or po) diphenhydramine or equivalent	Glucocorticoid (iv)* methylprednisolone or equivalent
1 st	1000 mg	50 mg	50 mg
2 nd	1000 mg	50 mg	50 mg

*This is in addition to the daily prednisone (or equivalent) therapy

Vital sign monitoring during Ofatumumab infusion:

Vital signs will be monitored every 30 (+/- 5) minutes as standard procedure during ofatumumab infusion, or more frequently if needed based on the clinician's judgment.

First Infusion of Ofatumumab:

The initial rate of the first infusion of ofatumumab (300mg at 0.3 mg/mL; 700mg at 0.7mg/mL; and 1000mg at 1mg/mL) should be 12 mL/h. If no infusion reactions occur the infusion rate may be increased as tolerated every 30 minutes, to a maximum of 400 mL/h, according to the following table. If this schedule is followed, the infusion duration will be approximately 4.6 hours.

Infusion rate at 1st ofatumumab infusion

Time	mL/hour
0 – 30 minutes	12
31 – 60 minutes	25
61 – 90 minutes	50
91 – 120 minutes	100
121 - 150 minutes	200
151 - 180 minutes	300
181+ minutes	400

*acceptable window surrounding each time frame for escalation of infusion rate is +/- 10 minutes.

Dose Modification

- If an infusion reaction develops, the infusion should be temporarily slowed or interrupted.

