- For Grade 4 infusion reactions, do not resume the infusion (subjects who experience a grade 4 toxicity at least possibly due to ofatumumab will not receive further doses of ofatumumab).
- For Grade 1, 2, or 3 infusion reaction, if the infusion reaction resolves or remains less than or equal to Grade 2, resume infusion with the following modifications according to the initial Grade of the infusion reaction:

Grade 1 or 2: Infuse at one-half of the previous infusion rate.

Grade 3: Infuse at a rate of 12 mL/hour.

Thereafter, the infusion rate may be increased as tolerated.

Subsequent Infusions of Ofatumumab:

If the previous infusion has been completed without grade ≥ 3 infusion-associated AEs, the subsequent infusion of ofatumumab (300mg at 0.3 mg/mL; 700mg at 0.7mg/mL; and 1000mg at 1mg/mL) can start at a rate of 25 mL/hour and may be doubled approximately every 30 minutes up to a maximum of 400 mL/h, according to the following table. Duration of the infusion will be approximately 4 hours if this schedule is followed. If the previous infusion has been completed with grade ≥ 3 infusion-associated AEs, the subsequent infusion should start at a rate of 12 mL/hour. However, actual dose delivered (e.g. 300mg, 700mg or 1,000mg dose cohort level) will not be modified on day 14 dose.

Dose Modification for subsequent infusions of Ofatumumab:

- If an infusion reaction develops, the infusion should be temporarily slowed or interrupted.
- For Grade 4 infusion reactions, do not resume the infusion (subjects who experience a grade 4 toxicity at least possibly due to ofatumumab will not receive further doses of ofatumumab)
- For Grade 1, 2, or 3 infusion reaction, if the infusion reaction resolves or remains less than or equal to Grade 2, resume infusion with the following modifications according to the initial Grade of the infusion reaction:

Grade 1 or 2: Infuse at one-half of the previous infusion rate.

Grade 3: Infuse at a rate of 12 mL/hour.

Thereafter, the infusion rate may be increased as tolerated.

Infusion rate at subsequent ofatumumab infusion

Time	mL/hour
0 – 30 minutes	25
31 – 60 minutes	50
61 – 90 minutes	100
91 – 120 minutes	200
121+ minutes	400

*acceptable window surrounding each time frame for escalation of infusion rate is +/- 10 minutes.

During infusion the patient should be monitored closely and appropriate measurements should be performed whenever judged necessary.

Technical details of Ofatumumab composition and dosing:

Medication

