Dose of Ofatumumab	Infusion bag size	Volume of NaCl to be removed from infusion bag	Volume ofatumumab (number of ofatumumab vials)
300 mg	1000 mL	15 mL	15 mL (3 vials, 5 mL/vial)
700 mg	1000 mL	35 mL	35 mL (7 vials, 5mL/vial)
1000 mg	1000 mL	50 mL	50 mL (10 vials, 5 mL/vial)

Ofatumumab Infusion Set up

Ofatumumab must be administered by i.v. infusion through an in-line filter and through a well-functioning i.v. catheter (i.v. cannula) into a vein in the arm (or other venous access) by an infusion pump.

Please Note: It is mandatory to use an in-line low protein binding 0.2 micron polyether sulfone filter for all IV dosing of ofatumumab drug product.

DO NOT ADMINISTER AS AN INTRAVENOUS PUSH OR BOLUS.

[figure not shown]
Ofatumumab should not be mixed with any other medication. If ofatumumab is to be dosed through an in-dwelling catheter, then, any previous medication should be removed by flushing with normal saline prior to dosing with ofatumumab.

Please note that the infusion site can be used for blood sampling only if there is no risk of contamination of the infusion needle with the saline, infusion solutions, or any other fluid(s). Only a newly inserted needle can be used for the predose blood samples.

- Check subject ID against the label on the infusion bag and ensure the expiry of the solution. The solution must be administered in its entirety to the subject within 24 hours from time of preparation.
- Attach the 1000mL infusion bag to the infusion set (if not done at the pharmacy).
- Attach the in-line filter to the infusion set (closest to the subject; see schematic below). **Note: The in-line filter must be used during the entire infusion.**
- Prime the infusion set and filter with ofatumumab (if not done at the pharmacy).
- In case of a problem with the filter (i.e. clogging/blockage), please change, re-prime the new filter, and continue the infusion.

- In case of problem with infusion set, follow local procedures.
- Collect the pre-dose blood samples, if required.
- Check the backflow from the i.v. cannula according to routine practice at site
- Set the pump at the initial infusion rate 12mL/hr for the first infusion and 25mL/hr for the subsequent infusions (see below infusion guidelines)

Infusion Set-Up Schematic

iii. Use of topical (non-systemic) therapies for chronic GVHD

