The use of topical agents for control of chronic GVHD manifestations is part of usual clinical care for affected patients. Common examples include various eye drops and artificial tears for ocular sicca, steroid or other immune suppressive agent mouth rinses for oral involvement, or topical steroid creams for mild cutaneous involvement. Use of these agents for patients on study will not be controlled or directed by this protocol. Rather, use of these agents will be directed by treating clinicians as part of usual clinical care. Use of these agents will be recorded in data capture on each study visit. Use of these non-systemic therapies will not inform study endpoints that include requirement for additional systemic immune suppressive therapies.

iv. Supportive antimicrobial prophylaxis on study

- i. All patients on study must receive antimicrobial prophylaxis per BMT guidelines and standards for the prevention of bacterial, viral, fungal, and pneumocystis infections.

V. STUDY OUTCOMES/ANALYSIS ENDPOINTS

1. Safety

a. Definition of DLT for phase I component:

- i. In the phase I study, dose escalation will proceed as previously described. The dose limiting toxicity (DLT) will be defined using CTCAE version 4.0 as the following:
 - Events occurring within 46 days of the last dose of drug (4 half-lives) that are:
 - a) Grade 4 infusion reactions,
 - b) Grade 4 constitutional symptoms at least possibly due to ofatumumab,
 - c) Grade 3 organ toxicities (neurologic, pulmonary, cardiac, gastrointestinal, genitourinary, hepatic, cutaneous) at least possibly due to ofatumumab,
 - d) Grade 4 neutropenia lasting more than 14 days
- ii. Importantly, known infusional toxicities of ofatumumab are managed appropriately with modification of infusion rate or temporary halting of infusion, as well as with supportive care including IV fluids, anti-histamines, and steroids.
- iii. Specifically, grade 1-3 infusion-associated adverse events defined by CTC version 4.0 are not considered DLT in this trial. The occurrence of grade 4 infusion-associated adverse event is considered DLT.
- iv. According to observed toxicities in the phase I component, the greatest dose tolerated in the dose escalation will be carried forward into the phase II component of the trial as the recommended phase II dose.
- v. Events clearly related to chronic GVHD, relapse of the primary hematological disorder, concurrent medication, or infection will not be included as a DLT.

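### At 12 mL/h the infusion restart rule is inverted: a grade 3 reaction resumes at 12 mL/h, a grade 1-2 reaction at 6 mL/h (minor safety correction)

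*Combined protocol and SAP*

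**What the plan says.** Everything here is in section IV.ii (Ofatumumab) of the combined protocol and SAP, unless noted.

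- **Start of the first infusion:** "The initial rate of the first infusion of ofatumumab (300mg at 0.3 mg/mL; 700mg at 0.7mg/mL; and 1000mg at 1mg/mL) should be 12 mL/h". The rate then rises every 30 minutes through 25, 50, 100, 200 and 300 to 400 mL/h.
- **Start of the second infusion:** normally 25 mL/h. If the previous infusion was completed with grade 3 or higher infusion-associated events, "the subsequent infusion should start at a rate of 12 mL/hour". A grade 4 toxicity at least possibly due to ofatumumab bars further doses, so in practice this start applies after an earlier grade 3 event.
- **Condition for restart after grade 1-3:** the infusion may resume "if the infusion reaction resolves or remains less than or equal to Grade 2".
- **Restart rate, by the initial grade:** "Grade 1 or 2: Infuse at one-half of the previous infusion rate"; "Grade 3: Infuse at a rate of 12 mL/hour". The same two lines stand in the Dose Modification blocks for the first and for subsequent infusions.
- **DLT definition (section V.1.a):** "grade 1-3 infusion-associated adverse events defined by CTC version 4.0 are not considered DLT in this trial".

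No part of the document sets a minimum rate, a cap relative to the previous rate, or an exception for a reaction at the lowest step.

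**The concern.** One restart rate is relative (half of what was running) and the other is absolute (12 mL/h). They keep the expected order only while half the running rate is above 12 mL/h. The opening step of the first infusion runs at 12 mL/h, so a severe reaction there is followed by a restart at the rate that provoked it, while a milder reaction at the same step gets a halved rate.

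The rest of the section points the other way. At every scheduled rate of 25 mL/h or more, grade 3 restarts slower than grade 1-2, and a grade 3 event in the first infusion lowers the start of the second from 25 to 12 mL/h. The inverted result looks like an oversight at the bottom of the scale.

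At stake is bedside safety for a patient who reacts at the lowest rate. No statistical property of the trial depends on it.

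**Working it through.** **Inputs (section IV.ii).** Infusion volume 1000 mL. First-infusion rates 12, 25, 50, 100, 200 and 300 mL/h for 30 minutes each, then 400. Second-infusion rates 25, 50, 100 and 200 mL/h for 30 minutes each, then 400. Restart rate = previous rate / 2 for grade 1-2, and 12 mL/h for grade 3.

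**The plan's own durations.** Duration = 0.5 h × number of steps before 400 mL/h + (1000 − volume given in those steps) / 400.

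- First infusion: volume = 0.5 × (12 + 25 + 50 + 100 + 200 + 300) = 343.5 mL. Duration = 3 + 656.5/400 = 4.64 h. The plan states about 4.6 h.
- Second infusion: volume = 0.5 × (25 + 50 + 100 + 200) = 187.5 mL. Duration = 2 + 812.5/400 = 4.03 h. The plan states about 4 h.

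Both reproduce, so the rate tables have been read correctly.

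**Where the two rules cross.** Previous rate / 2 = 12 gives a previous rate of 24 mL/h. Below that, grade 3 gets the faster restart.

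| Rate at reaction (mL/h) | Restart, grade 1-2 | Restart, grade 3 | Order |
|---|---|---|---|
| 6 (off schedule) | 3 | 12 | inverted |
| 12 | 6 | 12 | inverted |
| 12.5 (off schedule) | 6.25 | 12 | inverted |
| 25 | 12.5 | 12 | as expected |
| 50 | 25 | 12 | as expected |
| 100 | 50 | 12 | as expected |
| 200 | 100 | 12 | as expected |
| 300 | 150 | 12 | as expected |
| 400 | 200 | 12 | as expected |

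**Reach.** Among scheduled rates the inversion occurs only at 12 mL/h: the first of 7 steps in the first infusion, none of the 5 steps in the second-infusion table, and a second infusion started at 12 mL/h after a grade 3 event. It also applies to a recurrence at 12 mL/h after a grade 3 restart. The 30-minute step delivers 12 × 0.5 = 6 mL, or 0.6% of 1000 mL. With the ±10-minute window this is 4 to 8 mL (0.4% to 0.8%).

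**Off-schedule rates.** The halving rule itself creates rates below 24 mL/h: 6 mL/h after a grade 1-2 reaction at 12, and 12.5 mL/h after one at 25. If a recurrence is graded as a new reaction, which the text neither states nor excludes, a grade 3 recurrence at 6 mL/h would resume at 12 mL/h, twice the rate at which it occurred.

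**The case against.** The strongest reply is that the plan never says grade 3 must restart slower than grade 1-2. Its text also fits a different principle: after grade 3, go back to the starting rate. On that reading 12 mL/h is the intended lowest rate, the anomaly is the 6 mL/h that halving produces, and a 12 mL/h floor for grade 1-2 would be the simpler repair. This is a fair alternative account of intent, but it does not remove the conflict. The grade 1-2 line as written still sends a patient with the milder reaction to 6 mL/h, so the two lines disagree at this step on either reading.

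The second reply is that existing safeguards cover the risk: three-drug premedication, vital signs every 30 minutes or more often, slowing or interruption first, restart only at grade 2 or below, and supportive care. These are real, and they justify a low rating. None of them lowers the prescribed grade 3 restart rate at 12 mL/h.

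Third, no harm is demonstrated. Nothing in the documents shows that 6 mL/h is safer than 12 mL/h after a pause, or that grade 3 reactions occur at this step at all. That stands, and is why the rate should be confirmed clinically. The recurrence at 6 mL/h also needs a chain of unlikely events and an assumption about regrading, so little weight rests on it.

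**Conclusion.** The concern holds as a minor safety correction. For any reaction below 24 mL/h the rule as written gives the more severe grade the faster restart. At 12 mL/h, the only scheduled rate affected, a grade 3 reaction resumes with no reduction in rate. This follows directly from the text and needs no outside figure.

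Two things are less certain: that the intent is a slower restart for the more severe reaction, which is inferred from the rest of the section, and how often the situation would arise. Grade 1-3 infusion events do not count as DLTs, so dose escalation, the sample size, the error rates and the 6-month response endpoint are untouched.

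**What to change.** In both Dose Modification blocks, change the grade 3 line to: *restart at 12 mL/h or at half the rate before the reaction, whichever is lower*. The investigators and the drug supplier should confirm the rate.

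This gives 6 mL/h after a grade 3 reaction at 12 mL/h, cannot raise the rate after a recurrence at 6 mL/h, and leaves every scheduled step of 25 mL/h or more unchanged. It has one limit: below 24 mL/h, grade 3 then ties with grade 1-2 and is not slower. If the clinical team wants a strictly slower rate, or a minimum rate for repeated recurrences, it should say so in the same line.

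**Cost.** One line in each of two blocks, with no effect on analysis or accrual. For the patient the infusion is longer. Assume a grade 3 reaction at the end of the 12 mL/h step, 30 minutes at the restart rate, a return to the table, and no time counted for the pause:

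- First infusion, current rule (12, 12, 25, 50, 100, 200, 300, then 400): 349.5 mL in 3.5 h, plus 650.5/400 = 5.13 h.
- First infusion, proposed rule (12, 6, 12, 25, 50, 100, 200, 300, then 400): 352.5 mL in 4.0 h, plus 647.5/400 = 5.62 h.
- Difference: 29.6 minutes.

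For a second infusion started at 12 mL/h and then following its own table (an assumption), the change is from 5.00 h to 5.49 h, the same 29.6 minutes. Both are well inside the limit under Ofatumumab Infusion Set up: "The solution must be administered in its entirety to the subject within 24 hours from time of preparation".
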